5.5.6 Follow-up of Adverse Events

All AEs occurring during or after the subject has discontinued the study are to be followed up until resolved or judged to be no longer clinically significant, or until they become chronic to the extent that they can be fully characterized.

If during AE follow-up, the adverse event progresses to an "SAE", or if a subject experiences a new SAE, the Investigator must immediately report the information to the Sponsor.

5.5.7 Monitoring of Common Serious Adverse Events

Common serious adverse events are SAEs commonly anticipated to occur in the study population independent of drug exposure. SAEs classified as "common" are provided in [Appendix 3](#) **Most Common Serious Adverse Events** for reference. The list does NOT change your reporting obligations or prevent the need to report an AE meeting the definition of an SAE as detailed above. The purpose of this list is to alert you that some events reported as SAEs may not require expedited reporting to the regulatory authorities based on the classification of "common serious adverse events" as specified in [Appendix 3](#) **Common Serious Adverse Events**. The Sponsor will monitor these events throughout the course of the study for any change in frequency. Any changes to this list will be communicated to the participating investigational sites. Investigators must report individual occurrences of these events as stated in [Section 5.5.5](#) **Reporting of Serious Adverse Events**.

5.5.8 Procedure in Case of Pregnancy

If during the conduct of a clinical trial, a male subject impregnates his partner, the subject should report the pregnancy to the Investigator. The Investigator will report the pregnancy to the Sponsor or delegated CRO as an SAE.

5.5.9 Emergency Procedures and Management of Overdose

In the event of suspected overdose, refer to the approved Package Insert, SPC, or local product information supplied by the manufacturer for each agent.

5.5.10 Supply of New Information Affecting the Conduct of the Study

When new information becomes available necessary for conducting the clinical study properly, the Sponsor will inform all Investigators involved in the clinical study as well as the regulatory authorities. Investigators should inform the IRB/IEC of such information when needed.

5.6 Test Drug Concentration

Not applicable.

5.7 Other Measurements, Assessments or Methods

Not applicable.

5.8 Total Amount of Blood

Blood samples will be taken for the purposes of hematology, biochemistry and PSA analysis at Screening/tamsulosin hydrochloride run-in (Visit 1), Baseline (Visit 2), Week 4 (Visit 3), Week 8 (Visit 4), and Week 12/End of Treatment (Visit 5). It is anticipated the total amount of blood taken will not exceed 50 mL throughout the duration of the study.

6 DISCONTINUATION

6.1 Discontinuation of Individual Subject(s)

A discontinuation is a subject who enrolled in the study and for whom study treatment is permanently discontinued prematurely for any reason.

The subject is free to withdraw from the study treatment and/or study for any reason and at any time without giving reason for doing so and without penalty or prejudice. The Investigator is also free to terminate a subject's involvement in the study at any time if the subject's clinical condition warrants it.

If a subject is discontinued from the study with an ongoing adverse event or an unresolved laboratory result that is significantly outside of the reference range, the Investigator will attempt to provide follow-up until the condition stabilizes or no longer is clinically significant.

Subjects will be discontinued if they meet any of the following criteria:

- ALT or AST >3x ULN and total bilirubin >2x ULN
- ALT or AST >8x ULN on one occasion
- ALT or AST >5x ULN for more than 2 consecutive weeks
- ALT or AST >3x ULN with the appearance of fatigue, nausea, vomiting, right upper quadrant pain or tenderness, fever, rash and/or eosinophilia (>5%)

Subjects may also be discontinued for:

- Medically important adverse event(s)
- Protocol deviation(s) (e.g., subject took prohibited medication that in the Investigator's opinion, after discussion with the Medical Monitor, may negatively impact the subject's safety or demonstrated lack of cooperation in following protocol-specified procedures/instructions)
- Withdrawal of consent
- Investigator and/or Sponsor feel it is in the subject's best interest

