12.2 Appendix 2: Liver Safety Monitoring and Assessment

If laboratory testing for a subject enrolled in study and receiving study drug reveals an increase in serum aminotransferases (AT) to $>3X$ ULN, bilirubin $> 2 \times$ ULN, at least all four of the usual serum hepatic measures (ALT, AST, ALP, and TBL) must be repeated. Testing should be repeated within 48-72 hours of notification of the test results. Alerts will be generated by the central lab regarding moderate and severe liver abnormality to inform the Investigator, study monitor and study team. Subjects should be asked if they have any symptoms suggestive of hepatobiliary dysfunction.

Definition of Liver Abnormalities

Confirmed abnormalities will be characterized as moderate and severe where ULN:

Moderate	ALT or AST $> 3 \times$ ULN	or	Total Bilirubin $> 2 \times$ ULN
Severe*	$> 3 \times$ ULN	and	$> 2 \times$ ULN

In addition, the subject should be considered to have severe hepatic abnormalities for any of the following:

- ALT or AST $> 8 \times$ ULN
- ALT or AST $> 5 \times$ ULN for more than 2 weeks
- ALT or AST $> 3 \times$ ULN and INR > 1.5 (If INR testing is applicable/evaluated).
- ALT or AST $> 3 \times$ ULN with the appearance of fatigue, nausea, vomiting, right upper quadrant pain or tenderness, fever, rash and/or eosinophilia ($> 5\%$).

The Investigator may determine that abnormal liver function results, other than as described above, may qualify as moderate or severe abnormalities and require additional monitoring and follow-up.

Follow-up Procedures

Confirmed moderate and severe abnormalities in hepatic functions should be thoroughly characterized by obtaining appropriate expert consultations, detailed pertinent history, physical examination and laboratory tests. The site should complete the Liver Abnormality Case Report Form (LA-CRF) or an appropriate document. Subjects with confirmed abnormal liver function testing should be followed as described below.

Confirmed moderately abnormal LFTs should be repeated 2-3 times weekly then weekly or less if abnormalities stabilize or the study drug has been discontinued and the subject is asymptomatic.

Severe hepatic liver function abnormalities as defined above, in the absence of another etiology, may be considered an important medical event and may be reported as a Serious Adverse Event (SAE). The Sponsor should be contacted and informed of all subjects for

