whom severe hepatic liver function abnormalities possibly attributable to study drug are observed.

To further assess abnormal hepatic laboratory findings, the Investigator is expected to:

- Obtain a more detailed history of symptoms and prior or concurrent diseases. Symptoms and new onset-diseases should be recorded as ‘adverse events’ on the AE page of the (e)CRF. Illnesses and conditions such as hypotensive events, and decompensated cardiac disease that may lead to secondary liver abnormalities should be noted. Non-alcoholic steatohepatitis (NASH) is seen in obese hyperlipoproteinemic, and/or diabetic patients and may be associated with fluctuating aminotransferase levels. The Investigator should ensure that the medical history form captures any illness that pre-dates study enrollment that may be relevant in assessing hepatic function.
- Obtain a history of concomitant drug use (including non-prescription medication, complementary and alternative medications), alcohol use, recreational drug use, and special diets. Medications, including dose, should be entered on the concomitant medication page of the (e)CRF. Information on alcohol, other substance use, and diet should be entered on the LA-CRF or an appropriate document.
- Obtain a history of exposure to environmental chemical agents.
- Based on the subject’s history, other testing may be appropriate including:
 - acute viral hepatitis (A, B, C, D, E or other infectious agents)
 - ultrasound or other imaging to assess biliary tract disease
 - other laboratory tests including INR, direct bilirubin
- Consider gastroenterology or hepatology consultations.
- Submit results for any additional testing and possible etiology on the LA-CRF or an appropriate document.

Study Discontinuation

In the absence of an explanation for increased LFT’s, such as viral hepatitis, pre-existing or acute liver disease or exposure to other agents associated with liver injury, the subject may be discontinued from the study. The Investigator may determine that it is not in the subject’s best interest to continue study enrollment. Discontinuation of treatment should be considered if:

- ALT or AST > 8 × ULN
- ALT or AST > 5 × ULN for more than 2 weeks
- ALT or AST > 3 × ULN and TBL > 2 × ULN or INR > 1.5) (If INR testing is applicable/evaluated)
- ALT or AST > 3 × ULN with the appearance of fatigue, nausea, vomiting, right upper quadrant pain or tenderness, fever, rash and/or eosinophilia (> 5%).

Reference

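### Section 6.1 makes stopping mandatory at four ALT/AST criteria, Appendix 2 only asks sites to consider it at the same four thresholds, and nothing says which text prevails

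*Protocol*

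**What the plan says.** Protocol section 6.1 defines a discontinuation as the permanent, premature end of study treatment. It then gives two lists. The first, headed "Subjects will be discontinued if they meet any of the following criteria", has four entries, all based on ALT or AST: above 3x ULN with total bilirubin above 2x ULN; "ALT or AST >8x ULN on one occasion"; above 5x ULN for more than two consecutive weeks; and above 3x ULN with listed symptoms or eosinophilia. The second, headed "Subjects may also be discontinued for", holds the optional reasons, such as medically important adverse events, withdrawal of consent and the subject's best interest.

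Appendix 2 (section 12.2) covers liver monitoring. For aminotransferases above 3x ULN or bilirubin above 2x ULN it asks for a repeat: "Testing should be repeated within 48-72 hours of notification of the test results". It grades confirmed results as moderate or severe. Its closing part, on study discontinuation, lists liver triggers under "Discontinuation of treatment should be considered if". One of these adds an INR alternative to the bilirubin criterion: "ALT or AST > 3 × ULN and TBL > 2 × ULN or INR > 1.5".

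Section 5.4 points to Appendix 2 for evaluating, reporting and analysing drug-induced liver injury, and section 5.4.3.1 points to it for liver abnormalities and their monitoring. Section 6.1 does not mention Appendix 2, and the stopping list in Appendix 2 does not mention 6.1.

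**The concern.** Two current parts of the protocol give different instructions for the same laboratory result. The separation of mandatory from optional reasons in 6.1 looks deliberate, and the liver criteria are on the mandatory side. Appendix 2 moves the same criteria to the investigator's discretion. An investigator handling an abnormal liver result is sent to Appendix 2, so the weaker rule may be the one read at the moment of decision.

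Two things are at stake. The first is subject safety: a subject with results that Appendix 2 itself grades as severe could remain on drug although 6.1 requires stopping. The second is the deviation record. Section 8.1.6 makes it notifiable to the sponsor when a subject meets withdrawal criteria and is not withdrawn, and section 7.8 tabulates this as PD2. The same conduct counts as PD2 under 6.1 and is allowed under Appendix 2.

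**Working it through.** No sample size, power or error-rate figure bears on this point, so the check is a comparison of the two texts.

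**Step 1: match the criteria.** ALT/AST multiples are of ULN.

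| Section 6.1 (mandatory) | Appendix 2, study discontinuation (to be considered) | Same threshold? |
|---|---|---|
| >3x and bilirubin >2x | >3x and bilirubin >2x, with INR >1.5 as an alternative | Yes |
| >8x, one occasion | >8x | Yes |
| >5x for more than 2 consecutive weeks | >5x for more than 2 weeks | Yes |
| >3x with symptoms or eosinophilia >5% | >3x with symptoms or eosinophilia >5% | Yes |

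All 4 of the 4 criteria in 6.1 reappear in Appendix 2 at the same multiples. Two lose a word or phrase there (one occasion; consecutive), but the thresholds do not change.

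**Step 2: check that both govern the same action.** Section 6.1 defines discontinuation as permanently ending study treatment, and the Appendix 2 list is about discontinuing treatment. So it does not work to say that one text is about leaving the study and the other about stopping the drug.

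**Step 3: look for a precedence rule.** Sections 5.4, 5.4.3.1, 6.1, 7.8, 8.1.6 and Appendix 2 were read for one. None gives either text priority on stopping.

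**Step 4: compare with the severity grades.** Appendix 2 introduces its grading table with "Confirmed abnormalities will be characterized as moderate and severe where ULN", and then adds bullets under "In addition, the subject should be considered to have severe hepatic abnormalities for any of the following". The severe grade therefore has 1 table row + 4 bullets = 5 conditions. Four are the mandatory stops in 6.1. The fifth, ALT/AST above 3x ULN with INR above 1.5, is not in 6.1's mandatory list.

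**Step 5: follow one case through.** Take ALT above 3x ULN with bilirubin above 2x ULN. Under 6.1 the subject stops. Under Appendix 2 the site grades the result severe once confirmed, considers stopping, and may decide against it. If the subject stays on drug, 6.1 makes this PD2, while Appendix 2 has been followed.

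**The case against.** The best reply is that the texts can be reconciled: a site that stops the drug complies with both, and no passage tells anyone to continue it. Section 6.1 is the natural home of withdrawal criteria, and 5.4 and 5.4.3.1 refer to Appendix 2 for evaluation and monitoring, not for stopping. Central-laboratory alerts reach the investigator, the monitor and the study team. Section 5.4 requires sponsor contact within 24 hours for a confirmed marked abnormality, and exclusion criterion 24 screens on raised liver enzymes at entry. All of this stands and keeps the consequence small. It does not settle the rule, because alerts bring a case to attention without saying whether stopping is required, and Appendix 2 does carry its own list of stopping triggers.

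A reader might infer more than the documents support, in four ways:

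- *Different thresholds.* The wording missing from Appendix 2 does not create any. A single value already meets an unqualified >8x ULN, and more than two weeks ordinarily means consecutive weeks.
- *Waiting for the repeat test.* Appendix 2 asks for a repeat within 48-72 hours and grades confirmed results, but does not say to delay stopping until then. Stopping on the first value and repeating the test are compatible.
- *A contradiction on INR.* The INR trigger is absent from 6.1's mandatory list, but 6.1's optional reasons already allow stopping for it. This is an omission.
- *An exemption for another cause.* Appendix 2 says that a subject without another explanation may be discontinued from the study. It is unclear whether that condition reaches the list of triggers, and the point does not rely on it.

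**Conclusion.** The point holds as a conflict between a mandatory and a discretionary stopping rule at four matching liver thresholds, with no statement of which prevails. It should be fixed because it concerns subject safety and decides whether retaining such a subject counts as PD2. That last step assumes that the liver criteria in 6.1 are the withdrawal criteria meant in 8.1.6, which is the natural reading although 7.8 and 8.1.6 do not cite 6.1.

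The size is modest. The protocol gives no expected number of cases; few are likely, and the sponsor would probably see them. The sample size and the primary analysis are unaffected. The missing qualifiers and the relation of the repeat test to stopping are minor wording alignments, not separate defects.

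**What to change.** In the study discontinuation part of Appendix 2, replace the sentence that introduces the triggers, together with the four triggers that match 6.1, by: *Study drug will be permanently discontinued if any Section 6.1 liver criterion is met.* Referring to 6.1 instead of repeating its list also carries over the two qualifiers. Align the preceding permissive sentence as far as it covers these triggers.

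Keep ALT/AST above 3x ULN with INR above 1.5 as an explicit trigger; otherwise the replacement would delete the only place where it is named as a reason to consider stopping. Give it the same status in both sections. Whether that status is mandatory or to be considered is for the safety team. If the team wants a confirmatory repeat before stopping, or an exemption when another cause is found, the same condition should stand in both sections.

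No visits or tests are added, since INR is already in the laboratory panel (Table 3). The cost is more than editing: section 8.3.3 requires a signed amendment, with written IRB/IEC approval before a change affecting subject safety is implemented, and sites must be notified at up to 100 centers. The current version is dated 22 January 2018 and the planned study period ends in 2Q2018, so the benefit shrinks the later the change is made.

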6.2 Discontinuation of the Site

If an Investigator intends to discontinue participation in the study, the Investigator must immediately inform the Sponsor.

6.3 Discontinuation of the Study

The Sponsor may terminate this study prematurely, either in its entirety or at any study site, for reasonable cause provided that written notice is submitted in advance of the intended termination. Advance notice is not required if the study is stopped due to safety concerns. If the Sponsor terminates the study for safety reasons, the Sponsor will immediately notify the Investigator and subsequently provide written instructions for study termination.

7 STATISTICAL METHODOLOGY

The statistical analysis will be coordinated by the responsible biostatistician of Astellas. A Statistical Analysis Plan (SAP) will be written to provide details of the analysis, along with specifications for tables, listings and figures to be produced. The SAP will be finalized before database softlock at the latest. Any deviations from the analysis planned in SAP will be justified in the Clinical Study Report (CSR).

Prior to Database Lock, a Final Review of Data and TLFs Meeting will be held to allow a review of the clinical trial data and to verify the data that will be used for analysis set classification. If required, consequences for the statistical analysis will be discussed and documented. A meeting to determine analysis set classifications may also be held prior to database hard lock.

In general, baseline is defined as the last measurement before the first dose of double-blind study drug. For variables based on the electronic diary, the 3 days of the diary recorded prior to Visit 2/Baseline (Week 0) will be used to derive these variables at baseline just as the 3 diary days before each post-baseline visit will be used to derive these variables at these visits.

The End of Treatment (EOT) visit is defined as the last post-baseline visit during the double-blind study period for which data is available. The EOT visit value for diary variables is the average or number of the diary measurements for Week 12, as applicable. If no Week 12 diary data measurements are available, then the last available earlier post-baseline average or number of the diary measurements within a designated visit window will be used (LOCF). Data from the EOT visit will be analyzed to account for subjects prematurely terminating the study and is regarded as the primary visit. The EOT visit will be Week 12/EOT (Visit 5) for subjects who complete the study.

All statistical comparisons will be made using a two-sided test at $\alpha = 0.05$ significance level and confidence intervals (CIs) will be reported with a coverage consistent with this significance level unless specified otherwise.

All efficacy and safety variables will be summarized using descriptive statistics. Continuous variables will be summarized using the descriptive statistics number of non-missing observations (N), mean, standard deviation (SD) or standard error (SE), minimum, median, and maximum unless specified otherwise. Categorical variables will be described using N and percent.

7.1 Sample Size

The primary endpoint for this study is change from baseline to end of treatment in mean number of micturitions per day based on a 3-day diary.

Based on subgroup analysis of prior OAB studies, 544 subjects (272 evaluable subjects per treatment group) provides 80% power to detect a reduction of 0.65 in the mean number of micturitions per day over placebo in the mirabegron group at an alpha level of 0.05. A standard deviation for change from baseline in micturitions of 2.7 was assumed.

If 85% of the randomized subjects are evaluable, 640 subjects should be randomized. With an expected drop-out rate of 35% by the end of the tamsulosin hydrochloride run-in phase (V2), 985 subjects need to be screened.

7.2 Analysis Set

Three main analysis populations will be defined: Full Analysis Set (FAS), Full Analysis Set - Incontinence (FAS-I), and Safety Analysis Set (SAF).

Detailed criteria for analysis sets will be laid out in Classification Specifications and the allocation of subjects to analysis sets will be determined prior to database hard-lock.

7.2.1 Full Analysis Set

The FAS will include all subjects who meet all of the following criteria:

- Subjects who took at least 1 dose of double-blinded study drug after Randomization,
- Reported at least 1 micturition in the baseline diary and at least 1 micturition post-baseline,

The FAS will be used for the summary of all baseline characteristics, including demographic, disease state data, prior medications, prior medical history and a statistical analysis of efficacy endpoints and QoL instruments.

7.2.2 Full Analysis Set - Incontinence (FAS-I)

The FAS-I will include all subjects who meet all of the following criteria:

- Subjects who took at least 1 dose of double-blinded study drug after Randomization,
- Reported at least 1 micturition in the baseline diary and at least 1 micturition post-baseline,
- Reported at least 1 incontinence episode in the baseline diary.

The FAS-I will be used for the analysis of incontinence episodes.

7.2.3 Safety Analysis Set (SAF)

The SAF will consist of all randomized subjects who received at least one dose of double-blind study medication. The SAF will be used for summarizing demographic and baseline OAB characteristics and safety data.

7.3 Demographics and Other Baseline Characteristics

Demographic and OAB baseline characteristics will be summarized using descriptive statistics by treatment group, mirabegron and placebo.

7.4 Analysis of Efficacy

Efficacy analysis will be conducted on the FAS and PPS. Incontinence episodes will be analyzed with the FAS-I. The interpretation of results from statistical tests will be based on the FAS.

7.4.1 Analysis of Primary Endpoint

7.4.1.1 Primary Analysis

The primary efficacy variable is change from baseline to end of treatment in mean number of micturitions per day based on a 3-day electronic diary. The primary analysis will be performed for the FAS at the EOT visit, i.e. Week 12 for subjects who complete the study or last post-baseline visit during the double-blind study period for subjects who discontinue early.

The hypothesis for comparison is as follows:

H0: Difference between mirabegron and placebo in change from baseline to end of treatment in mean number of micturitions per day based on a 3-day electronic diary is 0.

H1: Difference between mirabegron and placebo in change from baseline to end of treatment in mean number of micturitions per day based on a 3-day electronic diary is not equal to 0.

Change from baseline to end of treatment in mean number of micturitions per day will be analyzed using Analysis of Covariance (ANCOVA). The response variable will be the mean change in number of micturition episodes per day from baseline to end of the study with treatment group, geographic region, and age group as fixed factors and baseline as a covariate. Within the framework of this ANCOVA model, LS means and two-sided 95% CIs for the mean change from baseline within each treatment group will be provided. Differences in LS means between mirabegron and placebo will be derived together with 95% CIs and p-values. Further details may be found in the SAP.

